***Visit 2: Study Equipment Placement & Training and Data Collection Period.***

Visit 1 and 2 can be completed on the same day. All subjects will receive training on the use of the 1) CGM and 2) study-supplied commercially available activity monitor (e.g., Fitbit or similar device). New sensors will be issued to each subject; the CGM may be reused after it has been cleaned as required using a dilute mixture of bleach or another appropriate cleaning agent.

[figure not shown]
**Continuous Glucose Monitor Training**

1. An outpatient visit will be scheduled for training on the study CGM.
2. Female subjects of childbearing potential will perform a urine pregnancy test, unless Visit 2 follows immediately after Visit 1. If the test is positive, the subject will discontinue study participation. The subject will be asked to seek confirmation of the test and the appropriate medical care.
3. The subject will be supervised during the initial CGM sensor placement. A CGM sensor will be inserted as per manufacturer directions.
4. If the CGM device experiences a sensor failure while at home, the subject will replace the sensor. The study team will be available for questions or will provide any necessary guidance.
5. The subject will be taught how to calibrate the CGM per manufacturer's guidelines and if prompted by the DiAs system during the admissions. The subject will be asked to perform all required calibrations with fingerstick glucose measurements.
6. If the subject owns a personal laptop device, he/she will be asked to bring it to the visit for the study team to download specific software to be used during data collection. If the subject does not own a laptop device but owns a desktop computer, he/she will be provided with a memory drive storing the appropriate resources to be used at home.
7. The subject will be taught to look for skin irritation after sensor removal.
8. If the subject requires an MRI/CT or diathermy, the sensor will be removed from the patient and the reason for removal will be noted. This will not be an adverse event. The visit may be rescheduled.
9. The outpatient visit will last approximately 1-2 hours depending on prior knowledge of the equipment.
10. The subject will be given an instruction sheet with 24-hour contact information of the research team to address any problems or questions.
11. Unlimited additional appointments and telephone calls to the study team and study physician will be available.

**Data Collection Period**

1. Subjects will collect data for approximately 14 to 28 days prior to Visit 3 and Visit 4.

2. The CGM and insulin pump data will be analyzed by the study team at the end of the Data Collection Period, to determine the SI profile that will be used during the Experimental Admission (Visit 3 or 4). Special emphasis will be noted to the study subject that all meal information (i.e., carbohydrate quantity and insulin) must be recorded in their insulin pump.
3. Subjects will be instructed on how to download the equipment (i.e., personal insulin pump, personal glucometer, study CGM, study activity monitor). Subjects will be asked to provide downloaded data periodically during the data collection period (approximately one time per week) using a web-based diabetes management system (e.g., Diasend, CareLink Pro, etc. – Figure 2) and local diabetes device management software (e.g., Dexcom Studio). The study team will review subject data to ensure proper data collection. Study team will review quantity and quality of the data. Additional download requests may occur depending upon the quality of the data collected.
4. Subjects will be asked to wear the study activity monitor during the data collection phase, removing prior to bathing and participating in water activities. Subjects will also wear the activity monitor to collect information on activity, exercise, heart rate, and sleep. A study Gmail account will be established for each subject. The commercially available app associated with the activity monitor will be placed on the subject's smartphone or subject's personal laptop to facilitate weekly downloading of data. If the subject has an existing personal account with the commercially available activity monitor and the subject would prefer to use their existing personal account rather than creating an anonymous account, the subject will be allowed to do so and the study team would request access to that account.
5. Subjects will be advised to consistently use the bolus calculator (or "wizard") of their insulin pump, and not to use temporary basal rates to compensate for meals.
6. Subject may be asked to repeat up to 4 weeks of the Data Collection Period.
7. If the subject is unable to provide the downloaded data from home, the subject will be asked to return to the office so the study team can assist them.
8. The subject may return to the office at any time for additional support.
9. Subjects will be asked to consistently use insulin parameters such as insulin-to-carbohydrate ratio and correction factor to dose insulin for meals and corrections and avoid modifying their insulin therapy parameters (i.e., basal insulin, insulin-to-carbohydrate ratio and correction factor profiles) for the entire duration of the study. If a change in insulin therapy parameters is recommended or required, it will have to be approved by the study physician; in such scenario, the subject may be asked to extend the Data Collection Period per principal investigator judgement.
10. Visit 3 will take place no more than 100 days after the end of the Data Collection Period.

**Figure 2: Example of web-based diabetes management systems used for data upload (Diasend top, CareLink bottom)**

### **Visit 3 and 4: Research Admission (i.e., Hotel).**

The Experimental and Control Admission will be separated by at least 48 hours with a maximum of 100 days. The order of these two visits will be randomly selected. Subjects will be admitted to the research location at approximately 9:00AM and will be discharged after approximately 24 hours.

All procedures will be the same for Visit 3 and Visit 4 with the following exception:

- Insulin Boluses during the Control Admission: All meal and correction boluses during the control admission will be per the subject's usual insulin parameters. The two admissions will use consistent insulin-to-carbohydrate ratio, correction factor, and basal profiles.
- Insulin Boluses during Experimental Admission: The dinner meal bolus will be determined with the use of the SI-informed bolus calculator during the Experimental Admission. The calculations will be performed on a study smartphone (Diabetes Assistant, DiAs), approved by the study MD, and subsequently communicated to the subject. The suggested insulin bolus will be administered through the subject's personal insulin pump. The study physician will override the insulin dose computed with the use of the SI-informed bolus calculator at any time if he/she considers it is not safe for the participant subject in the following way:

- 1 The dinner insulin dose suggested by the SI bolus calculator will be  $\pm 30\%$  of the dose that the subject should receive while using his/her own insulin pump bolus calculator (usual care). This is by design of the SI bolus calculator.
- 2 If the licensed endocrinologist conducting the study considers the dinner dose suggested by the SI bolus calculator to be unsafe he/she will override this dose.
- 3 In order to avoid bias between the physicians involved, every effort will be made to have the primary MD supervising all the experimental admission.
- 4 Since the visits will be randomized, regardless of when the experimental visit occurs, the MD supervising the trial will look at the standard dose suggested by the DiAs system using the participant's insulin therapy parameters and will indicate that dose (control) if the assigned insulin dose suggested by the SI bolus calculator is deemed to be unsafe. This will be equal regardless of who is the physician supervising the visit. In this way any bias will be avoided since the criteria used by all MDs listed on this protocol will be the same.
- 5 During both visits, control and experimental, the same procedures will be followed. Therefore, the dose suggested by the DiAs system using the participant's insulin therapy parameters during the experimental admission to override the dose suggested by the SI bolus calculator, should be consider safe and usual care for that particular participant.

Visits 3 and 4 will be fully supervised by a research team located at the hotel and gym at all times and will be monitored and supervised by the primary physician. In the event that the primary physician could not be available for a particular visit, the backup MDs will cover. The team will consist of a minimum of one registered nurse (trained in the execution of the protocol as well as in the management of hypo- and hyperglycemia) and a technician (trained in the use and maintenance of the DiAs system). In addition, one of the study medical physicians, primary MD, and one senior engineer will be on call during the entire admission, with backup physicians and engineer available if the primary contact is unable to be reached.

The CGM used in the study is FDA-approved for the non-adjunctive measurement of blood glucose and will be remotely monitored in real-time during the entire admission (including exercise) by the study team via the DiAs Web Monitoring platform. The CGM readings will be the primary source of blood glucose levels. There are no protocol fingerstick blood glucose measurements other than at times of CGM calibration and if directed by the study team.

**Study Procedures that will occur during both Visit 3 and Visit 4 (Hotel):**

**Prior to Research Visit**

1. Subjects may be asked to insert a new CGM sensor up to 48 hours prior to the start of Visit 3 and Visit 4, per study staff judgement.

2. Subjects will be asked to avoid physical activity and alcohol consumption in the 48 hours prior to Visit 3 and Visit 4.
3. The study physician will review the data collected during the at home Data Collection Period and will determine the set of parameters to be used by the subject during the Experimental and Control Admission in order to optimize postprandial glycemic control.

#### **Procedures at beginning of Research Visit**

1. Subjects will meet the study team and check in to the research location at approximately 09:00AM, after a morning breakfast consumed at home per regular subject's habit.
2. The study team will confirm that the subject brought his/her insulin, insulin pump supplies, and regular medications. The study team will also confirm the absence of a febrile illness and may reschedule the admission if this criterion is not met.
3. Female subjects of childbearing potential will perform a urine pregnancy test. If positive, the subject will discontinue study participation. The subject will be asked to seek confirmation of the test and the appropriate medical care.
4. The study team will take the subject's vital signs, measure ketone concentration using the study ketone meter, and connect the DiAs system to the subject's CGM transmitter via Bluetooth connection (the DiAs is not connected to the subject's insulin pump, only to the CGM).

#### **Procedures during Research Visit (Figure 3)**

1. After checking in, subjects will be asked to conduct quiet activities (i.e., reading) until lunch is served.
2. **Lunch:** A lunch meal will be served at approximately 12:00PM. The subject will estimate the amount of carbohydrates in the lunch meal. The amount of carbs designated by the subject will be consistent between the Control and Experimental Admission.
3. **Exercise Session:** The subject will be transported to a local gym at approximately 2:00PM to perform a controlled exercise activity in the early afternoon, designed to alter insulin sensitivity in the late afternoon and evening. Exercise will start at approximately 2:30PM and will consist of 45 minutes of moderate intensity exercise (~70% maximum heart rate) divided in 3 periods of 15 minutes each.
4. Quiet activities will be conducted during the afternoon until dinner is served.
5. **Dinner:** A dinner meal will be served at around 7:00PM. The subject will estimate the amount of carbohydrates in the dinner meal. The amount of carbs designated by the subject will be consistent between the Control and Experimental admission. The dinner bolus will be computed with the insulin sensitivity-informed bolus calculator during the Experimental Admission. Should this dose be considered to be safe, the procedures detailed previously (pages 12 and 13) will be applied. The override dose indicated will be the one suggested by the DiAs system using the participant's insulin therapy parameters to avoid variability and/or discrepancies between the MDs listed in this protocol. Every effort will be made to have the primary physician supervising all admissions.

6. At approximately 10:00PM participants will be instructed to go to sleep and the following morning at approximately 9:00AM the subjects will be discharged after being offered breakfast with no dietary restrictions.
7. Subjects will be allowed to consume caffeine at breakfast before the admission and at the end of the admission before discharge; no caffeinated beverage consumption is allowed during the study admissions otherwise.
8. The subject will have access to ad lib glucose-free beverages.
9. All meal and correction boluses during the admissions will be based on CGM.
10. Fingerstick will occur prior to calibration of CGM if calibration is needed per manufacturer's guidelines or if it is prompted by the DiAs system. The subject may request any additional fingersticks as desired. Study personnel may also request fingersticks at their discretion.
11. Hypoglycemia treatment (e.g., glucose tablets, glucose gel/liquid, and a glucagon emergency kit) will be available for treatment at all times.
12. A study MD will be available for any clinical concerns and will approve the SI-informed meal bolus for dinner during the Experimental Admission.
13. The subject will be accompanied by a medically qualified staff member during the admissions.
14. Blood glucose will be monitored remotely during the entire duration of the admission.

#### **Procedures Related to Discharge**

1. At approximately 9AM, subjects will be discharged.
2. Subjects' vital signs will be checked.
3. The subject will resume his/her normal home insulin therapy.
4. The subject will be offered breakfast prior to discharge.
5. Subjects will be asked to check their blood glucose the following day and to monitor for possible symptoms of hypoglycemia since discharge.
6. Study staff will contact the subject by phone within 24-48 hours after discharge to enquire about AEs or BG <50 or >400 mg/dL.
7. Subjects may be asked to repeat up to two admissions (i.e., either 2x Visit 3 or 2x Visit 4) in the event that there is inadequacy of data collection during the admission, inaccurate CGM readings or the need to refine the optimization strategy based on the data collection period.

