**Statistical Considerations**

**1. Is stratification/randomization involved? Yes**

**► IF YES, describe the stratification/ randomization scheme.**

1. Randomization will be done at the Screening Visit and will be performed by simple randomization schedule (like flipping a coin)
2. Randomization will not be blinded; it will determine the order of the Experimental and Control Admissions after the initial 14-28 days of Data Collection

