**Power/Precision of the study to address major study endpoints:**

As a safety and feasibility study, this trial is not powered to a specific outcome. A sample size of 15 subjects has been chosen with the purpose of being able to compute the Cohen's  $d$  once the trial is completed. Cohen's  $d$  is defined as the difference between two means divided by a standard deviation for the data (standardized difference between two means), and will serve as effect size to appropriately power the subsequent main trial.

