**4. What is your plan for primary variable analysis?**

We will compute CGM metrics with the primary outcome analysis of LBGI by CGM following dinner, comparing the Experimental Admission to Control Admission.

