**The subject may resume the study after the following problems are resolved:**

1. Correction of a malfunction of the system or controller once the problem is clearly identified and the system has been repaired
2. Loss of sensor data acquisition for more than three hours
3. If remote monitoring cannot be restored within 180 minutes, study staff will monitor it at least hourly.

[figure not shown]

Figure 3: Diagram of the study research visit

**2. If this protocol involves study treatment, explain how a subject will be transitioned from study treatment when they have completed their participation in the study.**

The optimized bolus calculator will be used during the Experimental Admission (either Visit 3 or Visit 4, according to the randomization). After the Experimental Admission is completed, subjects will resume their usual insulin parameters.

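### An admission with sound data may be rerun to refine dosing, and the plan does not say which admission then supplies the primary LBGI and Cohen's d

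*Combined protocol and SAP*

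**What the plan says.** **Repeats.** Procedures Related to Discharge, item 7, lets subjects "repeat up to two admissions (i.e., either 2x Visit 3 or 2x Visit 4", and so on, for inadequate data collection, "inaccurate CGM readings or the need to refine the optimization strategy based on the data collection period". It gives no criterion, decision-maker or time limit for the last ground. It also does not define the strategy. That could be the insulin-sensitivity-informed calculator and its profile (question 2 after the stopping rules says "The optimized bolus calculator will be used during the Experimental Admission") or the therapy parameters.

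**When dosing is settled.** Data Collection Period, item 2, has the sensitivity profile determined at the end of that period. Prior to Research Visit, item 3, says the study physician "will determine the set of parameters to be used by the subject during the Experimental and Control Admission", after reviewing the home data.

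**What the team can see.** Statistical Considerations, question 1: "Randomization will not be blinded; it will determine the order of the Experimental and Control Admissions". The section on Visits 3 and 4 says the CGM "will be remotely monitored in real-time during the entire admission (including exercise) by the study team via the DiAs Web Monitoring platform".

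**What is analysed.** Statistical Considerations, question 4, specifies the "primary outcome analysis of LBGI by CGM following dinner, comparing the Experimental Admission to Control Admission". Under Power/Precision, Cohen's d "will serve as effect size to appropriately power the subsequent main trial". Neither place mentions repeats, and no analysis set is defined.

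**The concern.** The analysis plan is written as if each participant has one Experimental and one Control Admission. Item 7 means that some may have two of one kind. The CGM trace that yields the primary outcome has by then been seen by people who know which bolus method was used, and one ground for repeating does not depend on any fault in the data.

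If a disappointing post-dinner trace makes refinement seem more necessary, and the rerun then takes the place of that admission, regression to the mean alone improves the Experimental result, even when the refinement achieves nothing. The quantity exposed is Cohen's d, and the protocol gives the ability to compute d as the purpose of choosing 15 subjects. An inflated d would make the main trial too small.

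**Working it through.** The plan has no figure of its own on this point. The check has two parts: whether the gap exists in the text, and what it could do under stated assumptions.

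**1. Text.** A repeat presupposes an admission already run. Had the profile and parameters been settled at the times the protocol sets, no later refinement would be due. The third ground therefore operates only when something is reopened after an admission. Statistical Considerations, questions 2 to 5, contain no rule choosing between the first and a later admission.

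**2. Assumptions for the illustration.** Only n = 15 comes from the protocol. The rest is assumed:
- LBGI is normal, and d is taken on the paired difference, scaled to SD 1, so each admission has within-person variance 1/2.
- The between-person share of LBGI variance, ρ, is 0, 0.5 or 0.7.
- The one Experimental Admission with the highest LBGI is rerun and replaced, with no real benefit from refinement.

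**3. Shift in the mean difference by hand.** The expected maximum of 15 standard normal values is 1.736. A rerun loses only the within-person part of that excess, so

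shift = (1/15) × 1.736 × √((1 − ρ)/2)

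- ρ = 0: 0.1157 × 0.707 = 0.082
- ρ = 0.5: 0.1157 × 0.500 = 0.058
- ρ = 0.7: 0.1157 × 0.387 = 0.045

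**4. Mean d by simulation (200,000 trials per cell).**

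| ρ | true d 0: no rerun | true d 0: one worst rerun | true d 0.5: no rerun | true d 0.5: one worst rerun |
|---|---|---|---|---|
| 0 | 0.00 | 0.09 | 0.53 | 0.64 |
| 0.5 | 0.00 | 0.06 | 0.53 | 0.60 |
| 0.7 | 0.00 | 0.05 | 0.53 | 0.58 |

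The 0.53 is ordinary small-sample bias: 0.5 / (1 − 3/55) = 0.529. Mean d rises by more than the hand-calculated shift because replacing an extreme value also shrinks the SD in the denominator. At a true d of 0.5 the increase is 0.58 − 0.53 = 0.05 to 0.64 − 0.53 = 0.11. The SD of d from trial to trial is about 0.3.

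**5. Contrasting cases.**
- Reruns chosen at random: no shift (0.00 and 0.53).
- The worst admission rerun in each arm: mean d is 0.00 at a true d of 0, and about 0.55 to 0.58 at 0.5. The mean difference stays at 0.50, so that smaller inflation comes from the reduced SD.

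**6. Another definition of d.** The protocol does not say which SD divides the difference. With the average of the two conditions' SDs, within-person correlation 0.3 to 0.7, and about 1 in 15 of the highest Experimental results replaced, mean d goes from about 0.52 to 0.58–0.64.

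**The case against.** The strongest objection is that item 7 ties refinement to the data collection period, not to how an admission turned out. That stands as a reading of the words. A reader might infer that the protocol provides for reruns prompted by poor results; it does not. It permits them, because nothing prevents them and the trace has been seen by the time this ground can apply.

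Other stronger readings also fail:
- **Unequal parameters.** A reader might infer that a rerun could use different ratios, correction factors or basal rates from the other admission. Inclusion criterion 7 and the Visit 3 and 4 section require the same ones in both, and item 7 does not waive that.
- **More repeat routes.** Glycemic Guidelines, item 3, and item 2 of the individual stopping criteria also allow repeats or rescheduling. They cover interrupted participation, often with no completed admission to compete with the repeat. The first follows high ketones, which are not a sign of high LBGI.
- **A quantified shortfall in the main trial.** Larger shifts appear if more worst-case reruns are assumed, and they can be turned into sample sizes. The documents give no rerun frequency, no SD and no main-trial design, so such figures would only restate the assumptions.

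It is also fair that this is a pilot with no stated test or significance level, and that a shift of 0.05 to 0.11 is well below the sampling SD of d. But sampling error goes in both directions, whereas this selection goes in one. The 30% limit on bolus modification and the physician override restrict the dose, not which admission is counted.

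**Conclusion.** The concern holds in a limited form. The protocol permits a technically sound admission to be rerun after its outcome trace has been seen unblinded, and no rule says which admission enters the primary LBGI and Cohen's d. Both facts can be read directly from the text.

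Whether bias follows depends on conduct the documents do not describe. It needs reruns that tend to follow poor Experimental results and replace them. With outcome-unrelated reruns there is none; with equal reruns in both arms there is none at a true d of 0 and a smaller inflation at 0.5. The illustrated move from about 0.53 to 0.58–0.64 rests on one worst-case rerun in 15, normal data and an assumed variance share. It is not an estimate for this trial. This is a cheap improvement, worth making because d is the figure carried forward to the main trial.

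**What to change.** **Preferred.** In Procedures Related to Discharge, item 7, delete refinement as a ground for repeating and keep the two technical grounds. Fix and date the sensitivity profile and therapy parameters before Visit 3, and use them for any technical repeat.

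**If the ground is kept.** Add to Statistical Considerations, question 4: *The first technically valid admission of each type is analysed for LBGI and Cohen's d; validity is judged only on data completeness and CGM accuracy, and any admission repeated after refinement is reported separately as exploratory.* Because staff watch the CGM live, set the completeness and accuracy limits in writing before the first admission.

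**One exception.** If safety requires a physician-approved parameter change after Visit 3, repeat both admissions under the new parameters and make that pair primary. Report how many participants this affects and show their superseded results, since replacing a pair after seeing it can also select.

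**Cost.** A short text amendment. Retuned admissions cannot enter the primary result. A participant under the exception needs one extra 24-hour admission if the change comes before Visit 4, and two if it comes after. This should be rare.
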